#### 9.1.1.3 Maximum Tolerated Dose

The MTD is defined as one dose level below the dose level where  $\geq 2$  of 6 subjects experience a DLT. If  $\leq 1$  of 6 subjects in all dose cohorts experience a DLT, then an MTD has not been reached.

#### 9.1.1.4 Selection of the Recommended Phase 2 Dose

The RP2D will be selected based on integrated evaluation of safety, tolerability, clinical benefit, PK, and PD data, for all dose levels tested. The investigator and sponsor will jointly evaluate the data and select the RP2D.

Selection of the RP2D will take place after the last subject in the Dose Escalation part completes the Treatment Phase ([Section 9.1.3.2](#)).

The RP2D will be selected according to the following guidelines:

1. The RP2D will not exceed the MTD.
2. Toxicities other than DLTs will be considered, including: AEs assessed as related to study drug treatment but not considered dose-limiting, the nature and frequency of toxicities, and the emergence of any specific category of toxicities.
3. Evidence of clinical activity, as available.
4. Available pharmacodynamic data.
5. Consideration will be given to select RP2D dose that will sustain E7046 exposure above IC50 or IC90 values for EP4 inhibition for the duration of dosing period.

If two or more potential RP2D dose levels cannot be distinguished using the criteria above, cohort expansion (see below) may take place at up to 2 dose levels to obtain data for up to 6 additional subjects per dose level. Selection of RP2D will be based on this larger dataset.

If serious related toxicities are observed in later cycles beyond Cycle 1 a reduction of the MTD and/or RP2D may be considered. This determination will be made by the investigators and the sponsor physician, taking into account all available data.

### 9.1.2 Cohort Expansion

An expansion cohort of 6 to 16 subjects will be enrolled and treated at the RP2D after completion of the dose escalation part. The objective is to further evaluate safety and efficacy of E7046 at the RP2D and further characterize PK and PD. Subjects will be selected from the same tumor types as in the dose escalation part.

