**Table 1 Dose Cohorts in E7046 Dose-Escalation**

Dose level	No. of Subjects	E7046 Dose
-1	6	75 mg QD
1	6	125 mg QD
2	6	250 mg QD
3	6	500 mg QD
4	6	750 mg QD

QD = once daily.

The schema for dose escalation is adopted and modified from the traditional 3+3 design and is shown in [Figure 3](#). Dose limiting toxicities are defined in [Section 9.1.1.2](#).

Enrollment for first dose cohort (125 mg QD): (see Figure 3 Panel B)

In the first cohort, staggered dosing will be employed as described below.

Suspected severe immune reactions (ssIR) are defined as listed in the CTCAE v4.03 "Immune System Disorders", including Allergic Reaction, Anaphylaxis, and Cytokine Release Syndrome.

*First 3 subjects (Subjects 1, 2, and 3)*

- Initially one subject (Subject #1) will be enrolled and dosed.
  - If after 14 days of dosing no suspected severe immune reactions are observed, another 2 subjects (Subjects # 2 and 3) will be enrolled and dosed.
  - If within the first 14 days, Subject #1 experiences a suspected severe immune reaction, another subject (Subject #2) will be enrolled and dosed.
    - If after 14 days of dosing no suspected severe immune reactions are observed for Subject #2, another subject (Subject #3) will be enrolled and dosed.
    - If within the first 14 days, Subject #2 also experiences a suspected severe immune reaction, enrollment in this dose cohort will stop. A lower dose level of 75 mg QD (Dose Level -1) may be tested. Enrollment of the 6 subjects at Dose Level -1 will follow the same staggered schema as described for Dose Level 1.

*Next 3 subjects (Subjects 4, 5, and 6)*

- After evaluation of the first 3 subjects for DLTs after 21 days (Cycle 1), enrollment will continue as follows:
  - If  $\leq 1$  of 3 first subjects experiences DLTs in Cycle 1, the remaining 3 subjects (Subjects # 4, 5, and 6) in the first cohort will be enrolled and treated.
  - If  $>1$  of 3 first subjects experiences DLTs in Cycle 1, a lower dose level of 75 mg (dose level -1) will be tested, following the same enrollment schema as described for Dose Level 1.

Enrollment of subsequent dose cohorts:

[figure not shown]
- There will be no staggered dosing after the first dose cohort, however the subject enrolment will be controlled so that no more than one subject will be dosed on the same day.
- If  $\geq 2$  of 6 subjects in any dose cohort experiences a DLT, then dose escalation will be stopped.

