Subjects who for reasons other than drug related toxicity or a DLT, fail to complete 75% of the planned total dose in Cycle 1, (equivalent to 16 out of 21 days) will be replaced.

Assessment of DLTs will be discussed and agreed to by investigator(s) and sponsor physician prior to proceeding to the next dose level, and the decision will be documented.

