#### 9.1.3.2 Treatment Phase

**Treatment Phase** is Cycle 1 (Day 1 - 21) where evaluable subjects will be assessed for DLT.

At the end of the Treatment Phase subjects continue to the Extension Phase.

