#### 9.4.1.1 Dose modifications

Toxicity will be managed by concomitant medication (as appropriate), treatment interruption, dose reduction and treatment discontinuation, or a combination of these.

Dose reduction is allowed for all subjects during all cycles of treatment.

Subjects who experience a DLT in Cycle 1 may be allowed to continue study drug at a reduced dose after discussion with sponsor Medical monitor if this is judged to be in their best interest (see dose modification guidelines below).

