#### Guidelines for dose adjustments

During E7046 treatment, dose interruptions and reductions due to toxicity will be implemented according to the instructions presented in [Table 2](#). Any dosage interruptions of more than 3 days should be discussed with sponsor's medical monitor to establish if longer dose interruption is needed.

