**Table 2 E7046 Dose Reduction and Interruption Instructions**

[figure not shown]
E7046-related Toxicity a	During Therapy	Approximate dose adjustment b
Grade 1		
All occurrences	Continue E7046 treatment	Maintain dose level
Grade 2		
1st occurrence		Maintain dose level
2nd occurrence (same toxicity)		Reduce by one dose level of starting dose
3rd occurrence (same toxicity)	Interrupt E7046 until resolved to Grade $\leq 1$ or baseline c	Reduce by two dose levels of starting dose
4th occurrence (same toxicity)		Discuss with Sponsor
Grade 3		
1st occurrence		Reduce by one dose level of starting dose
2nd occurrence (same toxicity)	Interrupt E7046 until resolved to Grade $\leq 1$ or baseline c	Reduce by two dose levels of starting dose
3rd occurrence (same toxicity)	Discontinue E7046 treatment	Not applicable
Grade 4: Discontinue E7046d		

- a. Excluding alopecia and nausea, vomiting or diarrhea not receiving adequate treatment.
- b. Subjects assigned to dose level -1 (75 mg) will not be dose-reduced and will not continue treatment under the conditions in which dose reduction is mandated. Subjects assigned to dose level 1 (125 mg) can only be dose-reduced by one dose level and will not continue treatment under the conditions in which reduction of two dose levels is mandated.
- c. A delay of E7046 for more than 7 days due to any treatment-related toxicity must be discussed with the sponsor before treatment can be resumed.
- d. Exclude Grade 4 hematologic toxicity of less than 72 hours duration.

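### The 6 to 16 subject expansion at the RP2D has no cumulative DLT limit that requires a cohort-level decision while enrolment continues

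*Protocol*

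**What the plan says.** **Rules that use a count.** Protocol 9.1.1.1 gates the first cohort on the DLTs in its first 3 subjects. For all cohorts, if at least 2 "of 6 subjects in any dose cohort experiences a DLT, then dose escalation will be stopped". Section 9.1.1.3 sets the MTD from the same 2-of-6 line. Section 9.1.1.2 adds: "Assessment of DLTs will be discussed and agreed to by investigator(s) and sponsor physician prior to proceeding to the next dose level".

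**The expansion.** "An expansion cohort of 6 to 16 subjects will be enrolled and treated at the RP2D after completion of the dose escalation part" (Protocol 9.1.2). The section gives size, dose, purpose and tumour types, and nothing on DLT limits. Section 9.7.2 says these subjects serve to confirm the RP2D.

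**Safeguards without a count.**
- In Cycle 1, "evaluable subjects will be assessed for DLT" (9.1.3.2), with no restriction to the escalation part.
- A subject with a Cycle 1 DLT "may be allowed to continue study drug at a reduced dose after discussion with sponsor Medical monitor" (9.4.1.1).
- "Any dosage interruptions of more than 3 days should be discussed with" the sponsor's medical monitor (9.4.1.1), and a toxicity delay of more than 7 days "must be discussed with the sponsor before treatment can be resumed" (Table 2, note c).
- GI bleeding, colitis, irAEs and diarrhea above Grade 2 always count as serious (9.5.5.2). SAEs are reported within 24 hours (9.5.8.1).
- "If serious related toxicities are observed in later cycles beyond Cycle 1 a reduction of the MTD and/or RP2D may be considered" (9.1.1.4).
- The sponsor may discontinue the study at any time (11.11).

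**Analysis.** SAP 5.6.2 has DLTs reviewed once all subjects at a dose level have finished Cycle 1, and lists the result. Protocol 9.7.1.6 tabulates DLTs by dose level, under the dose escalation endpoints. No interim analysis is planned (Protocol 9.7.3, SAP 6).

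**The concern.** Six subjects say little about a DLT rate, so a dose can pass escalation and still be too toxic. The expansion is meant to confirm the dose, yet no accumulating result in it is defined as a failure to confirm.

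The provisions that might fill the gap do not:
- The 2-of-6 rule has one stated consequence, stopping escalation, which is over by then. It also gives no threshold for as many as 16 subjects.
- The joint DLT agreement is tied to moving to the next dose level, a step the expansion does not have.
- The provision for reducing the RP2D is discretionary and concerns toxicity after Cycle 1, whereas the DLT window is Cycle 1.
- The SAP review, if applied to the expansion, falls after its enrolment is complete, and no action follows from it.

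At stake is the number of subjects in a first-in-human study who may be enrolled at a poorly tolerated dose before anyone has to look at the cumulative rate.

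**Working it through.** **The plan's own figure.** 4 cohorts × 6 = 24. Then 24 + 6 = 30 and 24 + 16 = 40, matching the stated 30 to 40 subjects. The documents give no target or expected DLT rate, so every true rate p below is an assumption. The protocol itself expects moderate toxicity (9.1).

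**Step 1: what a pass leaves open.** The one-sided 95% exact upper limit solves P(X ≤ x | n = 6, p) = 0.05.
- 0 of 6: 1 − 0.05^(1/6) = 0.393.
- 1 of 6: (1−p)^6 + 6p(1−p)^5 = 0.05 gives p = 0.582.

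**Step 2: chance that a dose passes.** P(X ≤ 1) = (1−p)^6 + 6p(1−p)^5. At p = 1/3 this is 0.088 + 0.263 = 0.351. Expected DLTs in 16 further subjects are 16p.

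**Step 3: an example limit.** Pause when cumulative DLTs at the RP2D reach one third of evaluable subjects, rounded up, from n = 7. The 6 escalation subjects are included. The limit is checked after each expansion subject, by exact enumeration given at most 1 DLT in the first 6 and no add-on subjects. *Avoided* means 16p minus mean expansion DLTs if every pause becomes a permanent stop and 3 (or 5) more subjects enter before the triggering DLT is known. *Per trial* multiplies by the chance of passing.

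| True rate | Passes | 16p | Pause | Avoided given pass, lag 3 / 5 | Per trial, lag 3 / 5 |
|---|---|---|---|---|---|
| 10% | 0.886 | 1.6 | 2% | 0.02 / 0.01 | 0.01 / 0.01 |
| 15% | 0.776 | 2.4 | 6% | 0.07 / 0.05 | 0.06 / 0.04 |
| 20% | 0.655 | 3.2 | 13% | 0.20 / 0.15 | 0.13 / 0.10 |
| 25% | 0.534 | 4.0 | 25% | 0.44 / 0.33 | 0.23 / 0.18 |
| 33.3% | 0.351 | 5.3 | 49% | 1.12 / 0.83 | 0.39 / 0.29 |
| 40% | 0.233 | 6.4 | 68% | 1.92 / 1.43 | 0.45 / 0.33 |
| 50% | 0.109 | 8.0 | 89% | 3.42 / 2.60 | 0.37 / 0.28 |

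The pause column includes pauses that come too late to spare anyone. Pauses that still leave a subject to enrol after the lag, at 33/40/50%, are 45/63/84% (lag 3) and 39/56/77% (lag 5).

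**Step 4: sensitivity.** With a lag of 8 the per-trial figures at 33/40/50% fall to 0.16/0.18/0.16. If all 16 are enrolled before any DLT is known, nothing is avoided. For a 6-subject expansion and a lag of 3, a pause leaves someone to enrol in 8/13/21%, and DLTs avoided given a pass are 0.03/0.05/0.11. With a lag of 5 they are zero.

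**The lag.** No document gives it. For scale, 40 subjects over an 18-month study (5.1), less 6 cycles of follow-up (9.7.1), is 40 / (548 − 126 days) × 21 = 2.0 subjects per 21-day window. Expansion enrolment may be faster.

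**The case against.** The strongest reply is that the people who would take the decision already have the information. SAEs arrive within 24 hours, the likely toxicities are always serious, DLT subjects continue only through the medical monitor, and the sponsor can stop at any time. A pause rule therefore adds a prompt and no new information, while the benefit figures assume that every pause becomes a stop. The per-trial figures also treat passing 1-of-6 as becoming the RP2D, although 9.1.1.4 weighs other toxicity, activity, PD and exposure as well, and lower doses must have passed first. The gain is near nil at the low rates the protocol expects and at the permitted minimum of 6 subjects. The 58% limit is an extreme: a dose with that true rate passes only 5% of the time.

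All of that stands as a limit on size, so the benefit is stated as an upper bound and shown at low rates too. It does not remove the gap. Case-by-case contact manages single subjects, and nothing says at what cumulative rate enrolment must wait.

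Three stronger readings are tempting. A reader might infer that expansion subjects are unmonitored, or that DLTs are not assessed in them. The reporting rules and section 9.1.3.2 show otherwise. A reader might take 1 to 3 DLTs avoided per expansion as the expected gain. That holds only for a dose whose true rate is about 33 to 50% and which passed by chance. And a reader might extend the count to 6 + 6 + 16 = 28 subjects, but 9.1.1.4 describes its up to 6 additional subjects per dose level as cohort expansion, so they may not be extra to the 16.

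**Conclusion.** The gap is real and narrow: no cumulative DLT count in the expansion requires a cohort-level decision during enrolment. Closing it is a cheap improvement in subject protection that should be made. It does not show that the RP2D is likely to be too toxic, or that safety oversight is absent.

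For 16 subjects, a lag of 3 to 5, every pause a stop and the passing dose becoming the RP2D, the upper bound is about 0.3 to 0.45 DLTs avoided per trial at true rates of 33 to 50%, and 0.01 to 0.23 at 10 to 25%. It is smaller if enrolment resumes after review, and essentially nil for a 6-subject expansion. The true rates, the lag and the one-third limit are assumptions. The documents fix none of them.

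**What to change.** **Protocol 9.1.2.** State that new expansion enrolment pauses when cumulative Cycle 1 DLTs among DLT-evaluable subjects at the RP2D (escalation plus expansion) reach a pre-stated limit, until the investigators and sponsor physician document a decision. After resumption, re-check at each further DLT. An example limit of at least one third from n = 7:

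| Evaluable at RP2D | 7–9 | 10–12 | 13–15 | 16–18 | 19–21 | 22–24 |
|---|---|---|---|---|---|---|
| Pause at | 3 | 4 | 5 | 6 | 7 | 8 |

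Continue at one third if add-on subjects are enrolled. One third mirrors the 2-of-6 line. The sponsor may choose another limit.

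**Which DLTs count.** Use the definition and replacement rule in Protocol 9.1.1.2 (7 or more missed days; 16 of 21 days). SAP 13.3 differs (more than 4 missed days; 17 of 21 days), so the count could otherwise depend on the document used.

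**Reporting.** Extend the DLT tabulation in Protocol 9.7.1.6 and the listing in SAP 5.6.2 to expansion subjects.

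**Cost.** A short amendment which, as a safety change, needs health-authority submission and IRB/IEC approval (Protocol 11.1), plus a SAP clarification. No new committee or data are needed. The operational price is a review pause in about 2, 6, 13 and 25% of 16-subject expansions at true rates of 10, 15, 20 and 25%.

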### 9.1.3 Study Phases

The study will consist of three phases for each subject: Pretreatment Phase, Treatment Phase, and Extension Phase.

A schematic of the 3 Phases is shown in [Figure 4](#).

PHASE	Pretreatment		Treatment			Extension		
PERIOD	Screening	Baseline	Treatment Cycle 1			Treatment Continuation (Cycle 2 and beyond)	EOT	Follow -Up
Day	-28 to -1	-3 to -1	D1	D8	D15	D1	D8 (C2-6 only)	
VISIT	1	2	3	4	5	6, 8 etc	7, 9 etc	98 99

EOT = End of Treatment

### Figure 4 Study Design

#### 9.1.3.1 Pretreatment Phase

The Pretreatment Phase is 28 days before the first day of dosing, and consists of:

- A **Screening Period** spanning Day -28 to Day -1, to obtain informed consent, assess disease characteristics at study entry, and to establish protocol eligibility
- A **Baseline Period**, which consists of the last 3 days of the Screening period (Day -3 to Day -1), to establish baseline characteristics and confirm eligibility to start treatment.

#### 9.1.3.2 Treatment Phase

**Treatment Phase** is Cycle 1 (Day 1 - 21) where evaluable subjects will be assessed for DLT.

At the end of the Treatment Phase subjects continue to the Extension Phase.

### 9.1.3.3 Extension Phase

The Extension Phase consists of 2 periods:

- **Treatment Continuation Period**, during which subjects will continue in Cycle 2 and beyond to receive the same treatment they received during the Treatment Phase.  
The **Treatment Continuation** period will start at the end of the Treatment Phase and will end with the completion of the Off-Treatment Visit (which will occur within 30 days after the last administration of the study drug). It consists of study drug treatment on a 21-day cycle, regardless of dose interruptions. Subjects will undergo safety and efficacy assessments as defined in Schedule of Procedures ([Section 9.5.6.1](#)) . Subjects will discontinue the study drug and become Off-Treatment at the time of disease progression, development of unacceptable toxicity, withdrawal of consent or termination of the study program.
- A **Follow-Up Period**, for study assessments after discontinuation from study treatment.  
The **Follow-up Period** will begin the day after the Off-Treatment Visit and will continue as long as the study subject is alive until the completion of the primary analysis, unless the subject withdraws consent or until the sponsor terminates the study. Subjects, who discontinue study treatment without disease progression will continue to be followed and undergo tumor assessments every 6 weeks until disease progression or until the start of another anticancer treatment. In the follow-up period, subjects will be treated by the investigator according to the prevailing local standard of care. Subjects will be followed every 12 weeks ( $\pm 1$  week) for survival, performance status and subsequent anticancer treatments. The sponsor may decide to terminate survival follow-up anytime during the Extension Phase or when all subjects have discontinued study treatment.

## 9.2 Discussion of Study Design

This is an open label, multicenter, Phase 1 study that will be conducted in 2 parts: a dose escalation part and a cohort expansion part.

E7046 will be administered as a single agent orally once daily (QD) continuously in 21-day cycles. Animal PK studies have shown that a once daily schedule administered continuously is likely to be adequate to maintain systemic concentrations of E7046 in an efficacious range, at the doses planned ([Section 7.1.3.2](#)).

E7046 will be tested in sequential escalating dose cohorts of 6 subjects per cohort, to identify a MTD and/or a RP2D ([Section 9.1](#) for detailed discussion of the rationale for this design). Preclinical studies suggest that toxicities are anticipated to be moderate in the dose range planned to be studied, and that an MTD may not be reached. In this case, the RP2D will be selected based on integrated evaluation of safety, tolerability, clinical benefit, PK, and PD data, for all dose levels tested. Dose cohorts of 6 subjects each will be enrolled at each of the 4 dose levels to be tested, rather than employing a traditional 3+3 design. This number of subjects per cohort is expected to provide sufficient data for selecting a RP2D in the absence of an MTD.

The starting dose of 125 mg (first-in-human dose) is the human equivalent dose of 1/9 the minimally toxic dose in preclinical species. Based on preclinical PK/PD data, this dose was also projected to be in the efficacious range based on sustaining exposure at IC50 – IC90 of EP4 inhibition in vitro and on effectiveness in animal tumor models. The maximum dose of 750 mg is >5 fold the starting dose of 125 mg, the latter being an anticipated efficacious dose. The maximum dose is also limited by the number of capsules to be ingested (6 capsules, with current capsule strength) being close to the maximum feasible number of capsules that could be taken at a time.

This study will enroll subjects with tumor types that are characterized by high levels of myeloid infiltrate. The expected action of E7046 is to inhibit immunosuppressive cells of myeloid lineage. Preclinical work showed that E7046 had antitumor activity in six syngeneic tumor models with significant intratumoral monocytic cell infiltration, but not in other two tumor models with minimal monocytic cell infiltration. Thus, this selected population is considered appropriate for the expected mechanism of action of E7046.

### 9.3 Selection of Study Population

Approximately 30 to 40 subjects in total will be enrolled: 24 in the Dose Escalation part and 6 to 16 in the expansion cohort. Subjects who do not meet all of the inclusion criteria or who meet any of the exclusion criteria will not be eligible to receive study drug.

#### 9.3.1 Inclusion Criteria

Subjects must meet all of the following criteria to be included in this study:

1. Age  $\geq$ 18 years.
2. Eastern Cooperative Oncology Group (ECOG) Performance Status of 0 or 1.
3. Life expectancy  $\geq$ 12 weeks.
4. Subjects must have any of the following tumor types, confirmed by available pathology records or current biopsy, that is advanced, nonresectable, or recurrent and progressing since last antitumor therapy, and for which no alternative standard therapy exists:  
pancreatic adenocarcinoma, renal clear cell carcinoma, SCCHN, NSCLC, colorectal cancer (CRC), hepatocellular carcinoma (HCC), ovarian serous epithelial cancer, bladder transitional cancer, cervical cancer and triple-negative breast cancer
5. Prior chemotherapy or immunotherapy (tumor vaccine, cytokine, or growth factor given to control the cancer) must have been completed at least 4 weeks before study drug administration, and all AEs have either returned to baseline or stabilized.
6. Prior definitive radiation therapy must have been completed at least 6 weeks before study drug administration and the irradiated lesions should show evidence of progression if they are intended to be considered target lesions. Prior palliative radiotherapy must be completed at least 2 weeks before study drug administration. The radiotherapy related side effects must have resolved before the study entry. No radiopharmaceuticals (strontium, samarium) will be allowed within 8 weeks before study drug administration.
7. Subjects must have accessible tumors and consent to repeated biopsy for performance of correlative tissue studies.
8. Must have at least one measurable lesion per irRECIST ([Appendix 1](#)):
  - a. At least 1 lesion of  $\geq$ 10 mm in the longest diameter for a non-lymph node or  $\geq$ 15 mm in the short-axis diameter for a lymph node that is serially measurable according to irRECIST using computerized tomography/magnetic resonance imaging (CT/MRI).
  - b. Lesions that have had definitive external beam radiotherapy or locoregional therapies such as radiofrequency (RF) ablation or brachytherapy must show evidence of progressive disease to be deemed a target lesion.
9. Prior treated brain or meningeal metastases must be without evidence of progression (confirmed by MRI) for at least 8 weeks and off immunosuppressive doses of systemic

steroids (>10 mg/day prednisone or equivalent) for at least 4 weeks before study drug administration.

10. Immunosuppressive doses of systemic medications, such as steroids or absorbed topical steroids (doses >7.5 to 10 mg/day prednisone or equivalent) must be discontinued at least 2 weeks before study drug administration.
11. Subjects with prior Hepatitis B or C are eligible on the condition that subjects have adequate liver function as defined by Inclusion Criterion #16 and Exclusion Criterion #5.
12. Left ventricular ejection fraction (LVEF) >50% on echocardiography or multiple gated acquisition (MUGA) scan.
13. Adequate renal function defined as serum creatinine <1.5 × ULN (or use SI units or calculated creatinine clearance  $\geq 50$  mL/min per the Cockcroft and Gault formula [[Appendix 3](#)]).
14. Adequate bone marrow function:
  - a. Absolute neutrophil count (ANC)  $\geq 1500/\text{mm}^3$  ( $\geq 1.5 \times 10^3/\mu\text{l}$ )
  - b. Platelets  $\geq 100,000/\text{mm}^3$  ( $\geq 100 \times 10^9/\text{L}$ )
  - c. Hemoglobin  $\geq 9.0 \text{ g/dL}$
15. Adequate liver function:
  - a. Total bilirubin  $\leq 1.5 \times$  upper limit of normal (ULN) except for unconjugated hyperbilirubinemia of Gilbert's syndrome.
  - b. Alkaline phosphatase, alanine aminotransferase (ALT), and aspartate aminotransferase (AST)  $\leq 3 \times$  ULN ( $\leq 5 \times$  ULN if subject has liver metastases). If alkaline phosphatase is  $>3 \times$  ULN (in absence of liver metastases) or  $>5 \times$  ULN (in presence of liver metastases) AND the subject also is known to have bone metastases, the liver-specific alkaline phosphatase must be separated from the total and used to assess the liver function instead of total alkaline phosphatase
16. Adequate blood coagulation function as evidenced by an International Normalized Ratio (INR)  $\leq 1.5$ .
17. Willing and able to comply with all aspects of the protocol.
18. Provide written informed consent prior to any study-specific screening procedures.
19. Females must not be lactating or pregnant at screening or baseline (as documented by a negative beta-human chorionic gonadotropin [ $\beta$ -hCG] test with a minimum sensitivity of 25 IU/L or equivalent units of  $\beta$ -hCG). A separate baseline assessment is required if a negative screening pregnancy test was obtained more than 72 hours before the first dose of study drug. All females will be considered to be of childbearing potential unless they are postmenopausal (at least 12 months consecutive amenorrheic, in the appropriate age group, and without other known or suspected cause) or have been sterilized surgically (ie, bilateral tubal ligation, total hysterectomy, or bilateral oophorectomy, all with surgery at least 1 month before dosing). Females of childbearing potential must not have had unprotected sexual intercourse within 30 days prior to study entry and must agree to use a highly effective method of contraception, from the last menstrual period

prior to initiation of treatment, during Treatment Cycles, and for 30 days after the final dose of study treatment, and have a male partner who uses a condom. Highly effective contraception includes:

- a. Double barrier methods of contraception such as condom plus diaphragm or cervical/vault cap with spermicide.
- b. Placement of an intrauterine device.
- c. Established hormonal contraceptive methods: oral, injectable, or implant.

Females who are using hormonal contraceptives must have been on a stable dose of the same hormonal contraceptive product for at least 4 weeks prior to dosing and must continue to use the same contraceptive during the study and for 30 days after study drug discontinuation.

Female subjects exempt from this requirement are subjects who practice total abstinence or have a male partner who is vasectomized with confirmed azoospermia. If currently abstinent, the subject must agree to use a double barrier method as described above if they become sexually active during the Treatment Cycles, and for 30 days after study drug discontinuation

20. Male subjects must have had a successful vasectomy (confirmed azoospermia) or they and their female partners must meet the criteria above (ie, not of childbearing potential or practicing highly effective contraception and use a condom throughout the study period and for 90 days after study drug discontinuation).

